Second, we propose that SAV will engage different aspects of the corticostriatal circuits. SAV is traditionally a non-mindful cognitive strategy that promotes positive emotions through focused attention on pleasurable thoughts or sensory experiences.⁶⁰⁻⁶² Importantly, positive emotions are linked to activity within two other critical corticostriatal structures: the ventromedial prefrontal cortex (vmPFC), which is associated with the regulation of positive emotions⁶³⁻⁶⁶, and the nucleus accumbens (NAc), which is associated with reward valuation in human and animal studies.⁶⁷⁻⁶⁹ Indeed Speer et al.⁷⁰ showed that NAc and vmPFC function were significantly augmented during a basic savoring task, and NAc function correlated with the experience of positive emotions.

We plan to use these data to inform a follow-up study in which we combine MB and SAV and determine whether the combination optimizes the engagement of corticostriatal circuits during noxious stimulation.

4. Study Procedures

- a. Study design, including the sequence and timing of study procedures (distinguish research procedures from those that are part of routine care).

Overview of Study

We aim to demonstrate that MB promotes lOFC and putamen activation and SAV promotes NAc and vmPFC activation during noxious thermal stimulation among RA patients. We will execute a randomized controlled trial (RCT) comparing two arms: SAV, and sham MB in 40 RA patients (n = 20 per group). Originally, we also randomized participants to a third arm (MB). However, due to the disruption of the COVID-19 pandemic, we will no longer randomize to MB, in order to optimize our ability to complete the project on budget. The screening and intervention sessions will take place either via secure remote video conference (e.g., Zoom), or at Johns Hopkins Bayview Medical Center, as dictated by fluid laboratory density needs and participant safety precautions. There will also be a post-intervention fMRI task, which will take place at University of Maryland-Baltimore (UMB). The fMRI visit is the only that will take place at UMB.

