Sample Size Estimation: The analysis plan outlined below includes simplistic models that ensure that we capture the main effects that we hypothesized. While more complex statistical models are plausible, the use of one- and two-sample t-tests allows us to confidently determine a sample size that achieves statistical

[figure not shown]

Figure 1. Left column: **The MB group significantly reduced pain ratings when compared to the sham-MB and control manipulations. *The sham-MB group significantly reduced pain ratings when compared to the control group. Right column: In the presence of noxious heat, mindfulness-based analgesia was associated with greater activation in the bilateral orbitofrontal cortex (OFC) and right putamen.

power based on previous work. Notably, this study is not powered for efficacy or effectiveness, but rather to observe intervention group differences on activation of corticostriatal circuits.

Zeidan and colleagues have repeatedly demonstrated^{18,19} that sample sizes ≥ 15 (per group) reliably detect the neural mechanisms supporting meditation-induced analgesia in both between and within-person designs. To more specifically power the study, we ran a preliminary analysis from a colleague's data set ([name]) and examined subjects' behavioral and neural (arterial spin labeling fMRI) pain responses before and after each group's respective interventions (MB vs. sham). As shown in Figure 1, while both sham MB and MB reduced pain, they did so via distinct brain mechanisms: MB-based analgesia was associated with greater activation in the bilateral OFC and right putamen¹⁸. We used a neuroimaging-based power calculation software (Neuropowertools) and entered the contrast of parameter estimates from the preliminary analysis in Figure 1. Our simulation indicated that $n=17/\text{group}$ will provide over 80% power to test the hypotheses that interventions have differential effects on corticostriatal activation during noxious thermal stimulation, correcting for multiple comparisons. To account for loss of degrees of freedom due to random cluster effects associated with the randomization, we will target $n=20/\text{group}$ ($N=40$ total) for the R61 phase.

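### The power of over 80% at 17 per group was computed for mindful breathing versus sham, but it is used to justify a trial of savoring versus sham that has no power input of its own

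*Combined protocol and SAP*

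**What the plan says.** All references are to the combined protocol and SAP.

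- **Section 7c, Sample Size Estimation.** The study is described as not powered for efficacy or effectiveness, "but rather to observe intervention group differences on activation of corticostriatal circuits". The power input is a preliminary analysis of a colleague's arterial spin labeling data on MB and sham, in which "MB-based analgesia was associated with greater activation in the bilateral OFC and right putamen". The authors "entered the contrast of parameter estimates from the preliminary analysis in Figure 1" into Neuropowertools. They report that 17 per group, corrected for multiple comparisons, "will provide over 80% power to test the hypotheses that interventions have differential effects on corticostriatal activation during noxious thermal stimulation". The target is then raised to 20 per group, N=40, to allow for cluster effects.
- **Section 4a, Overview of Study.** The 40 patients are split 20 and 20 between SAV and sham MB. Under Screening and Randomization, MB is no longer allocated from July 2020.
- **Section 3, Background.** For savoring, "we propose that SAV will engage different aspects of the corticostriatal circuits". Section 4a names the regions: "SAV promotes NAc and vmPFC activation during noxious thermal stimulation among RA patients". MB is tied to the lateral orbitofrontal cortex and putamen.
- **Section 7c, Updated Statistical Approach due to Covid-19.** The MB arm was dropped and a new analysis plan written. Five subjects were excluded for artifact or motion, leaving 29 in the imaging analysis (15 SAV, 14 NMB). No new sample size or power statement is given.

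**The concern.** The sample size paragraph was updated to the two-arm total of 40, but its power figure still comes from the arm that was dropped. The text does not call the MB effect a stand-in for SAV, and Section 3 gives a reason to doubt that it is one, since different regions are expected to respond.

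The primary outcome (Section 7a) is brain function in the corticostriatal circuits, and this paragraph is its only quantitative sample size justification. The study is said to be sized for group differences in that outcome, and SAV versus sham is the only group difference left. A reader would naturally attach the power figure to that comparison. If a SAV-versus-sham contrast is reported and is null, the statement could make it look like evidence of no effect.

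**Working it through.** **1. Which comparison the figure belongs to**

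| | Power input (7c) | Current trial (3, 4a, 7c update) |
|---|---|---|
| Comparison | MB vs sham | SAV vs sham MB |
| Regions | bilateral OFC, right putamen | NAc, vmPFC (SAV hypothesis) |
| Effect size or SD printed | none | none |
| n per group | 17 | 20 planned; 15 and 14 analysed |

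The only SAV imaging evidence cited for these regions (Section 3) is qualitative. The supporting rule of at least 15 per group (7c) also comes from meditation studies, and 14 is below it.

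**2. Reproducing the plan's figure.** This is not possible. No effect size, peak heights, screening threshold or correction method is given for the simulation. The figure is not shown to be wrong for MB versus sham.

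**3. Shortfall.** The power is stated at 2 × 17 = 34, and 29 were analysed: 34 − 29 = 5 fewer (17 − 15 = 2 in SAV, 17 − 14 = 3 in NMB). I compare with 17 because the power is attached to 17; the step to 20 is for clustering, and no allowance for lost scans is stated. Against the target of 40 the gap is 11.

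**4. What the shortfall does to an MB-sized effect (guide only).** I used a single-endpoint two-sample t-test, two-sided α = 0.05, not the voxelwise cluster-corrected analysis. With standardized difference d, the noncentrality is λ = d / √(1/n₁ + 1/n₂), and power is the probability that a noncentral t with n₁ + n₂ − 2 degrees of freedom falls beyond ±t(0.975).

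- √(1/17 + 1/17) = 0.343, df 32; √(1/15 + 1/14) = 0.372, df 27.
- Exactly 80% at 17/17 implies d = 0.991 (λ = 2.89). At 15/14, λ = 2.67.

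| Power at 17/17 | d | Power at 15/14 |
|---|---|---|
| 80% | 0.991 | 72.9% |
| 85% | 1.060 | 78.5% |
| 86.3% | 1.080 | 80% |
| 90% | 1.147 | 84.5% |

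The first row was repeated with other significance levels (one-sided 0.05; Bonferroni over two or four regions; Z > 2.3; one-sided p < 0.001). Power at 15/14 then lies between 68.7% and 73.9%.

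**5. SAV versus sham.** No power can be computed. For scale only, with differences that I assume:

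| Assumed d | Power at 17/17 | Power at 15/14 |
|---|---|---|
| 0.5 | 29.3% | 25.5% |
| 0.8 | 61.9% | 54.6% |
| 1.2 | 92.4% | 87.5% |

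**6. What 15/14 can resolve, same basis.** The detectable d for 80% power is 1.08, against 0.99 at 17/17. With Bonferroni over four regions it is 1.32 at 15/14. The 95% confidence half-width, t(0.975, df) × √(1/n₁ + 1/n₂), is 2.052 × 0.372 = 0.76 SD at 15/14 and 2.037 × 0.343 = 0.70 SD at 17/17.

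**The case against.** The strongest reply is that nothing is hidden. The paragraph names MB versus sham as its source, and borrowing an effect from a related intervention is common in planning. That holds as far as disclosure goes. But the conclusion is worded for interventions in general and tied to the two-arm total, and the borrowing is never stated as an assumption.

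Second, the power is given as over 80%, a lower bound. If it was about 86% or more at 17/17, an MB-sized effect would keep 80% at 15/14. This stands: the shortfall does not prove that power fell below 80% for MB. Later scan losses also do not make a prospective statement inconsistent. The main defect is the wrong comparison; the losses add to it.

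Third, the updated fMRI section describes a pooled one-sample test and regressions, with no SAV-versus-sham test. So the risk of over-reading a null result is conditional. However, the mixed model earlier in Section 7c, with its heat by practice by condition interaction, is not expressly withdrawn, and Section 2 keeps the SAV objective.

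Fourth, the plan says that it is not powered for efficacy and calls the trial a small pilot. The first remark sits beside the claim to be powered for group differences in activation. The second is offered to justify the voxelwise threshold. Both soften the message, but neither withdraws the figure.

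Finally, the guide figures rest on a single-endpoint test whose SD unit depends on the contrast chosen. They should remain guides, and an interval from the actual data would be better.

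**Conclusion.** The concern holds, with high confidence. The stated power belongs to MB versus sham, while the N that it supports belongs to SAV versus sham, and the protocol itself expects the two interventions to act in different regions. No SAV power input exists in the documents. This is a mismatch of justification, not an arithmetic error.

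Both analysed arms are also below the 17 at which the figure was stated, by 2 and 3, if NMB is the sham arm. For an MB effect with exactly 80% power at 17/17, the guide figure at 15/14 is about 73%; it would be higher if the unreported power was higher. Power for SAV versus sham is unknown. On a single uncorrected endpoint, 15/14 gives 80% power only for differences of about 1.08 SD or more. The correction should be made, since the statement as written claims support that the current design does not have.

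**What to change.** In Section 7c, and in any report that repeats the figure:

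1. Limit the statement of over 80% power to MB versus sham at 17 analysable subjects per group.
2. State that SAV versus sham was not separately powered and that 15 and 14 were analysed. Define NMB.
3. If the MB effect is meant as a stand-in for SAV, say that it is an assumption and reconcile it with the different regions named in Sections 3 and 4a.
4. If a SAV-versus-sham contrast is reported, give the detectable effect at 15/14 as a guide (d about 1.08; two-sided 0.05, single endpoint, uncorrected; larger with any multiplicity correction). Interpret a null result through its observed confidence interval; about ±0.76 SD is the width to expect on the same basis.
5. Do not report 73% as the power for SAV.

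The cost is text only, with no extra patients, data or analyses. The stated power becomes less favourable, and the report has to say that SAV versus sham had no power calculation of its own.

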Recruitment. Individuals with physician-confirmed RA will be targeted in this study. Patients will be recruited via physician referral from the Johns Hopkins Arthritis Center, which is directed by Co-I [name], or via IRB-approved advertisements.

Screening and Randomization:

Telephone Screen: Participants will undergo an initial screen over the phone (or in person if they are initially identified in the Arthritis Center Clinic), prior to informed consent. Participants meeting initial screening criteria will be scheduled for a subsequent screening session.

Screening Session (Session 1): At the screening session (either remote or in person), participants will complete screening measures through REDCap and an interview with study staff. Participants will also be shown a video to familiarize themselves with noxious thermal stimuli.

Eligible participants will be randomized to MB, SAV, or Sham MB, and starting in July, 2020, participants will only be randomized to SAV or Sham MB. The female to male ratio in RA is approximately 2-3:1^{71,72}, and RA is diagnosed at a higher rate in White Americans compared to African Americans.⁷³ To ensure these differences are accounted for, we will test sex and race as covariates in analyses.

Intervention Visits: Intervention sessions for each randomized condition will be one-on-one with an interventionist. Sessions (4 total) will take place via secure remote video conference (e.g., Zoom) or in the Johns Hopkins Behavioral Medicine Research Lab (BMRL) as dictated by COVID-19 conditions, and will last 20-minutes. Intervention visits will be scheduled 2 per week, so that the entire intervention will be completed in 2 weeks.

Intervention Descriptions

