Mixed effects modeling will be used as the primary analytic strategy for the primary outcomes. In our group therapy RCT design, mixed effects models permit the modeling of cohort-level random effects, as well as heterogeneous variance/covariance matrices to account for potential alpha inflation due to cohort-level clustering. We will test regional signal change in each ROI using mixed effects models examining within-person main effects of thermal stimulus (HEAT; i.e., painful vs. warm) and skill practice (PRACTICE; i.e., rest vs. active practice in the scanner during delivery of thermal stimuli), and the between-person main effect of intervention condition (CONDITION; i.e., MB vs. Sham MB vs. SAV), as well as their requisite 2-way and 3-way interactions. Thus, the HEAT X PRACTICE X CONDITION interaction will test the extent to which CBF in each a priori corticostriatal region varies during the active practice of either Sham MB, or SAV, relative to rest. Planned comparisons will test each of the HEAT X PRACTICE 2-way interactions within intervention groups to aid in the interpretation of the 3-way interaction.

Updated Statistical Approach due to Covid-19

Due to COVID-19 restrictions, we had to drop one arm from the study (Mindful Breathing). As such, a new statistical analysis plan was developed that we detail in the next section.

fMRI Pre-Processing: Imaging analysis was conducted using Functional Magnetic Resonance Imaging of the Brain (FMRIB) Software Library (Center for FMRIB, University of Oxford, Oxford, UK) and ASL data processing toolbox. Five subjects were excluded from analysis due to detected image artifact or excessive motion. A total of 29 subjects (15 SAV group, 14 NMB) were included in the final imaging analysis. Subjects underwent 8 functional (ASL) runs during the MRI challenge session. The 8 ASL images that resulted from the runs represented combinations of two experimental conditions: Pain (nonpainful warm stimulus vs. noxious heat) and Practice (no meditation vs. meditation). These combinations occurred in the following order: 1. warm + no meditation; 2. noxious + no meditation; 3. warm + no meditation; 4. noxious + no meditation; 5. warm + meditation; 6. noxious + meditation; 7. warm + meditation; 8. noxious + meditation.

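### The primary mixed model is justified by therapy cohorts that a one-on-one trial does not define, and no participant-level error term is stated for the eight runs per person

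*Combined protocol and SAP*

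**What the plan says.** Section 4a (Intervention Visits): "Intervention sessions for each randomized condition will be one-on-one with an interventionist".

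Section 7c (Data Analysis): "Mixed effects modeling will be used as the primary analytic strategy for the primary outcomes". The reason given is "In our group therapy RCT design, mixed effects models permit the modeling of cohort-level random effects", together with "heterogeneous variance/covariance matrices to account for potential alpha inflation due to cohort-level clustering". The model is then set out for each region as "mixed effects models examining within-person main effects of thermal stimulus (HEAT; i.e., painful vs. warm) and skill practice", with CONDITION as a between-person effect and all two-way and three-way interactions. The three-way interaction is the test the text singles out.

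Section 7c (Updated Statistical Approach due to Covid-19): "Subjects underwent 8 functional (ASL) runs during the MRI challenge session". These form a 2 x 2 layout (warm or noxious, without or with practice) with two runs per cell. The final imaging analysis has 29 people, 15 and 14. This section announces a new analysis plan and lists a pooled one-sample t-test and regressions involving pain ratings. It has no cohort term, and as written it names no SAV-versus-sham contrast.

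Section 7c (Sample Size Estimation): 17 per group "will provide over 80% power to test the hypotheses that interventions have differential effects on corticostriatal activation during noxious thermal stimulation". The target becomes 20 per group "To account for loss of degrees of freedom due to random cluster effects associated with the randomization". No ICC, cluster size or number of clusters is given.

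**The concern.** One-on-one delivery and a group-therapy design cannot both describe this trial. Cohort is the only random effect named, and it has no unit, so an analyst cannot fit the model as written. The dependence that certainly exists, eight runs from the same brain, has no stated error term.

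This matters because the mixed-model text is the only place that specifies a test between the arms. Without a participant term the eight runs would count as independent observations, and the standard errors would be wrong for both the between-person and the within-person effects. The step from 17 to 20 per group also leans on clustering that is nowhere described.

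**Working it through.** **Sample size.** The 17 cannot be rebuilt, because the effect estimates, their SD and the threshold given to the software are not in the documents. For scale only, a two-sided two-sample t-test at 0.05 with 80% power and 17 per group implies d of about 0.99. At that d, 20 per group gives about 86% power.

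The step is 20/17 = 1.176. As a design effect, 1 + (m - 1) x ICC = 1.176 needs:
- m = 2: ICC = 0.176/1 = 0.176
- m = 4: ICC = 0.176/3 = 0.059
- m = 10: ICC = 0.176/9 = 0.020

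None of these is stated. With one person per session and no other cluster defined, m = 1, the design effect is 1 and 17 stays 17. A 15% loss allowance would also give 17/0.85 = 20, but no dropout rate is stated.

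**What happens if participants are ignored.** From the plan: 8 runs per person, 2 x 2 with two runs per cell, two-sided 0.05. Assumed: run-level residual variance 1; participant intercept variance t2, with ICC = t2/(1 + t2); and s2, the between-participant variance of the HEAT x PRACTICE effect, with factors coded +1/-1.

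A participant's mean has true variance t2 + 1/8, and the HEAT x PRACTICE contrast has s2 + 1/8. An analysis that ignores participants assigns (1 + t2 + s2)/8 to both. The ratios of true to assumed variance are therefore:
- CONDITION: R = (1 + 8 t2)/(1 + t2 + s2)
- three-way: R = (1 + 8 s2)/(1 + t2 + s2)

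Actual type I error is approximately P(|Z| > 1.96/sqrt(R)).

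| t2 (ICC) | s2 | CONDITION: R, error | Three-way: R, error |
|---|---|---|---|
| 0.43 (0.3) | 0 | 3.1, 27% | 0.70, 1.9% |
| 1 (0.5) | 0 | 4.5, 36% | 0.50, 0.6% |
| 2.33 (0.7) | 0 | 5.9, 42% | 0.30, 0.03% |
| 1 (0.5) | 0.25 | 4.0, 33% | 1.33, 9% |
| 0.43 (0.3) | 0.25 | 2.64, 23% | 1.79, 14% |
| 0.43 (0.3), plus HEAT and PRACTICE slopes of variance 0.1225 each | 0.25 | 4.43/1.924 = 2.30, 20% | 3/1.924 = 1.56, 12% |

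Simulation agrees. With 20 per arm and 4,000 null trials, t2 = 1 and s2 = 0 gave 36.9% for CONDITION and 0.75% for the three-way test; t2 = 1 and s2 = 0.25 gave 33.8% and 9.4%. With 15 versus 14 people and ICC 0.3 to 0.7, the ranges were 19% to 43% and 0% to 12%. The upper end for the three-way test depends on the assumed s2 and is not a bound, as the 14% row shows. Analysing one value per participant gave 4% to 6%.

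**Which participant structure is enough.** An intercept with HEAT and PRACTICE slopes leaves 5 residual degrees of freedom per person, one of which carries the HEAT x PRACTICE variation. The pooled residual has expectation 1 + 8 s2/5, so for the three-way test R = (1 + 8 s2)/(1 + 1.6 s2):
- s2 = 0.031: R = 1.19, error 7%
- s2 = 0.141: R = 1.73, error 14%
- s2 = 0.25: R = 2.14, error 18%

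Those slopes alone do not protect the key test. It also needs the participant HEAT x PRACTICE slope, which two runs per cell allow to be estimated.

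**The case against.** The strongest reply is that the plan never describes the faulty model. It calls HEAT and PRACTICE within-person and CONDITION between-person, which presupposes participant as the repeated unit. It says mixed models permit cohort effects, not that cohort is the only random effect. FSL first-level and second-level analysis also keeps participant as a level. This stands: a reader might infer that participants were ignored and that error rates near 40% apply to this trial, and the documents do not support that inference.

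The largest inflation also falls on the CONDITION main effect, which averages over warm and rest runs and is not the test the plan singles out. This too stands. For the three-way test the direction depends on s2, so a claim that it simply loses power would be wrong.

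A reader might further infer that no clustering exists. The text supports only that none is defined: a shared interventionist or enrolment batch could produce some. Nor does the sample-size paragraph mention cohorts or group therapy, so linking its cluster effects to them is an inference.

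Finally, the updated plan has no cohort term and, for its one-sample test, uses one averaged value per person. It does not settle the matter, because it does not expressly withdraw the mixed model and names no between-arm contrast in its place.

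**Conclusion.** The point holds as a contradiction and a gap in specification. Sections 4a and 7c disagree on how the interventions are delivered, the cohort effect has no unit, and the error term for the only stated between-arm test is not given.

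The error rates are conditional on fitting only the named random effect and on assumed variances, since the documents give none: about 19% to 43% for CONDITION and about 0% to 12% for the three-way interaction. They show why the structure must be written down; they do not describe an analysis known to have been done.

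The 17-to-20 rationale is undocumented. A reader might infer from this that the trial's target was too small, but 20 exceeds 17, so removing the cluster rationale does not lower planned power.

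**What to change.** 1. Reconcile section 4a with the Data Analysis text in section 7c on one-on-one versus group delivery.
2. Delete the cohort random effect, or replace it with a defined unit, such as interventionist if there was more than one.
3. Test HEAT x PRACTICE x CONDITION by a two-sample comparison of each participant's HEAT x PRACTICE contrast. Alternatively, use a mixed model with a participant intercept and participant slopes for HEAT, PRACTICE and HEAT x PRACTICE.
4. State whether this model remains primary after the Covid-19 update. If it does not, name the SAV-versus-sham contrast that replaces it.
5. In Sample Size Estimation, remove the random-cluster rationale unless a cluster unit and ICC can be given, and state the actual basis for 20 per group. It should not be relabelled as a dropout allowance unless that was the reason.

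The cost is wording in the plan. No new data or software are needed, and participant-level contrasts are simple to compute from the existing runs.

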- 2) Determine if SAV activates corticostriatal circuits during noxious stimulation.
- 3) Determine if MB and/or SAV evidence stronger activation of corticostriatal circuits during noxious stimulation.

3. Background (briefly describe pre-clinical and clinical data, current experience with procedures, drug or device, and any other relevant information to justify the research)

RA is a chronic systemic inflammatory disorder that is characterized by variable levels of pain that range from mild to debilitating and can flare unpredictably. RA affects approximately 3 million individuals in the United States, accounting for an annual cost of 46.7 billion dollars.^{1,2} Disease modifying anti-rheumatic drugs (DMARDs) are commonly used to manage RA symptoms by blocking pro-inflammatory cytokines, but symptom profiles and response to treatment vary substantially between patients³; up to 25%

of those receiving DMARDs show little or no improvement^{4,5}, and 20-40% of patients report chronic widespread pain that is poorly responsive to treatment.⁶⁻⁸ Additionally, pain flares can be unpredictable, varying substantially within patients^{9,10}, even during the course of pharmacotherapy.¹¹⁻¹³ Given these considerations, there has long been a keen interest in the use of non-pharmacological treatments as an adjunct to traditional pharmacotherapy to help patients “self-manage” pain and other RA symptoms.¹⁴⁻¹⁶ Indeed, research shows that modifiable psychological factors critically influence adaptation to RA.¹⁷

Mindfulness-based therapies are attractive candidate nonpharmacological interventions for the treatment of RA for several reasons. First, they attenuate the experience of acute pain at behavioral and corresponding neurobiological levels.^{18,19} Second, they are premised on sustaining non-reactive attention to the breath in the present moment²⁰, and are therefore well-suited to promote acceptance-based appraisals of *real-time* internal and external experiences.²¹ This type of skill is especially relevant to RA, given the flaring nature of RA pain.¹²⁻¹⁴ Third, they are associated with reductions in anxiety and depression²²⁻²⁴, which are common RA comorbidities that complicate treatment.^{25,26}

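### The three-way interaction named as the test in Section 7c does not measure what Objective 2 asks: it subtracts the warm-run practice effect, and no SAV-versus-Sham test within the noxious runs is named

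*Combined protocol and SAP*

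**What the plan says.** Objective 2 (Section 2) is: "Determine if SAV activates corticostriatal circuits during noxious stimulation". The Overview of Study in Section 4a puts the aim as showing that "SAV promotes NAc and vmPFC activation during noxious thermal stimulation among RA patients". Neither statement asks for the effect to be larger than it is under a warm stimulus.

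The Data Analysis text in Section 7c makes mixed-effects models the main strategy for the primary outcomes. The model has "within-person main effects of thermal stimulus (HEAT; i.e., painful vs. warm) and skill practice" (the latter defined as "rest vs. active practice in the scanner during delivery of thermal stimuli"), a between-person factor for arm, "as well as their requisite 2-way and 3-way interactions". It then says that "the HEAT X PRACTICE X CONDITION interaction will test the extent to which CBF in each a priori corticostriatal region varies" during active practice of Sham MB or SAV compared with rest. The follow-up is: "Planned comparisons will test each of the HEAT X PRACTICE 2-way interactions within intervention groups".

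The subsection headed Updated Statistical Approach due to Covid-19 then announces a new analysis plan, prompted by the loss of the MB arm. There the practice contrast compares meditation with no-meditation scans within the noxious runs only. Warm scans are subtracted only in the no-meditation runs, to map pain-related regions in all 29 analysed subjects together. No comparison of SAV with Sham is described, and the document does not say whether the mixed-model text is withdrawn.

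**The concern.** The quantity matching Objective 2 is (practice minus rest) CBF in the noxious runs, SAV minus Sham. The three-way interaction takes that quantity and subtracts its counterpart from the warm runs. The sentence in Section 7c describes an arm difference in practice versus rest, which is a PRACTICE × CONDITION effect, and attaches it to a different term. The planned within-arm HEAT × PRACTICE comparisons make the same subtraction, so they do not repair the mismatch.

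Some warm-run effect is plausible on the protocol's own reasoning. Section 3 supports the SAV hypothesis with a study in which "NAc and vmPFC function were significantly augmented during a basic savoring task", described without mention of pain. The warm practice runs use the same skill. Any such effect shrinks the named test statistic.

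Two misreadings are at stake. A null three-way could be taken as evidence against the SAV hypothesis, and Section 3 says these data will inform a follow-up study. A positive three-way supports a claim about specificity to noxious heat, which is not what Objective 2 asks.

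**Working it through.** **1. The plan's own figure.** The sample size text in Section 7c gives 17 per group for over 80% power. It cannot be reproduced, because the effect size, SD and threshold inputs to the power software are not stated. Back-solving a two-sided 5% two-sample test at 17/17 for 80% power gives a standardised difference of 0.96 (normal approximation) or 0.99 (noncentral t). This shows only the implied effect. The text rests on one- and two-sample t-tests of effects during noxious stimulation, so the stated power does not refer to a three-way interaction.

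**2. What each term estimates.** Let P(h, arm) be practice minus rest CBF at heat level h. Put the SAV-minus-Sham difference in P at D under noxious heat and f×D under warm.

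- Noxious-run contrast: P(nox, SAV) − P(nox, Sham) = D
- HEAT × PRACTICE × CONDITION: D − f×D = (1−f)×D
- PRACTICE × CONDITION, averaged over heat: (D + f×D)/2 = (1+f)×D/2
- HEAT × PRACTICE within SAV, if Sham has no practice effect: (1−f)×D

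With D = 1 and f = 0, 0.5, 1, the three-way is 1, 0.5, 0; PRACTICE × CONDITION is 0.5, 0.75, 1; the noxious-run contrast is 1 throughout. The noxious-run contrast is PRACTICE × CONDITION plus half the three-way: (1+f)D/2 + (1−f)D/2 = D. It can therefore be recovered from the planned model.

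**3. Standard error.** Suppose a person's noxious and warm practice differences have equal SD σ and correlation r. The variance of their difference is 2σ²(1−r), so the SE of the three-way relative to the noxious-run contrast is √(2(1−r)): 1.41 at r = 0, 1.00 at r = 0.5, 0.77 at r = 0.7. The three-way has the larger SE only if r < 0.5.

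**4. Power.** Set the standardised effect so that the noxious-run contrast has 80% power (0.99 at 17/17, 0.91 at 20/20, 1.08 at 15/14), multiply it by (1−f)/√(2(1−r)), and apply the two-sided noncentral t at 5%. For example, at 17/17 with f = 0.5 and r = 0: 0.99 × 0.5/1.41 = 0.35, giving 17%.

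| f | three-way power, r = 0 | three-way power, r = 0.5 |
|---|---|---|
| 0 | 51% | 80% |
| 0.25 | 32% | 56% |
| 0.5 | 17% | 29% |
| 0.75 | 8% | 11% |
| 1 | 5% | 5% |

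The rounded figures are the same at all three sample sizes. They count rejections in either direction; counting only those favouring SAV, the f = 0.75 row becomes 7% and 10%. The 5% at f = 1 is the false-positive rate.

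**5. The analysed sample.** Holding the effect at 0.99, the noxious-run contrast has 86% power at 20/20 and 73% at the 15 and 14 analysed, whatever f is. At 15/14 with f = 1 and r = 0, the three-way has 5% and PRACTICE × CONDITION 95%; a simulation of 20,000 replicates gave 5% and 95.5%.

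**The case against.** Several stronger readings are tempting, and the documents do not support them.

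- **That Objective 2 cannot be answered.** The model fits every two-way term, PRACTICE × CONDITION carries a shared effect, and the noxious simple effect follows from the same fit. The defect is that neither is named as the test.
- **That the SAV effect cancels.** Cancellation is complete only at f = 1. The cited savoring result suggests some warm-run effect but says nothing about its size relative to noxious heat.
- **That the three-way is always noisier.** This holds only for r < 0.5. The updated text places all rest runs first (1–4) and all practice runs last (5–8), so drift or a general response to practice that varies between people would enter both differences and push r upwards. At r = 0.7 and f = 0 the three-way would have 95% power, more than the noxious-run contrast.
- **That the three-way is the declared primary endpoint.** Section 7a names brain function in the corticostriatal circuits. Section 7c singles out the three-way as the test but does not label it the primary endpoint.

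The best defence is the updated approach, whose practice contrast already avoids the warm subtraction. That stands as far as it goes. It supplies the within-person half of the needed contrast, but its regressions relate CBF to pain ratings and its one-sample test pools the arms on no-meditation scans. Only the mixed-model text gives arm as a model term, and the document does not say which text governs.

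**Conclusion.** The point holds in a limited form. Section 7c misdescribes the three-way interaction, and both that term and the planned within-arm comparisons depart from Objective 2 by subtracting the warm-run practice effect. The attenuation factor (1−f) is algebra and needs no assumption about effect size or variance. The power figures are illustrative: they assume 80% power for the noxious-run contrast, equal SDs for the two practice differences, and chosen values of f and r. Over the values shown, three-way power runs from 80% (f = 0, r = 0.5) down to 5% (f = 1).

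A null three-way would not refute the SAV hypothesis. A reader might infer that the trial data cannot address Objective 2; they can, through a contrast available from the planned model. What is missing is a named SAV-versus-Sham test of activation during noxious heat and a statement of which analysis text applies.

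**What to change.** 1. Name as the main test of Objective 2 the SAV-minus-Sham difference in (noxious practice minus noxious rest) CBF in the a priori regions, taken as a planned contrast from the mixed model.
2. Keep HEAT × PRACTICE × CONDITION as a secondary test of whether the effect is specific to noxious heat, and correct the sentence describing it.
3. State whether the mixed-model text or the updated approach governs. If the updated approach does, add the SAV-versus-Sham comparison there.
4. Disclose the timing. The updated subsection reports exclusions and analyses in the past tense, so this contrast must be reported as specified late.

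The cost is one extra planned contrast and a few sentences of text, with no new data. The downside is that a test specified at this stage carries less confirmatory weight.
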